1.1 Rationale for Conducting the Study

In addition to its use for the treatment of primary and secondary immunodeficiencies, IGIV is increasingly used for immunomodulating therapy in the treatment of patients with a variety of autoimmune and inflammatory neurological disorders.

IGIV is currently used as a standard treatment in patients with chronic inflammatory demyelinating neuropathies, for initiation therapy as well as for long-term treatment. However, clinical studies published so far focused on a loading dose of 2.0 g/kg IGIV and/or a standard maintenance dosage of 1.0 g/kg IGIV, without investigating different dosing response options. The ProCID study thus aims to confirm the published clinical results obtained with the 1.0 g/kg standard dose, and will in addition evaluate one higher and one lower dose, with the aim to offer CIDP patients a more adequately dosed and effective treatment policy. The safety and tolerability of the various dosages will also be investigated, since many patients need lifelong treatment.

IGIV can be used for therapy of all different types of CIDP. Corticosteroids may worsen pure motor CIDP in which IGIV is recognized as the first-line treatment.[13,14]

Corticosteroids were the first treatment introduced for CIDP.[15] Several non-randomized studies and one randomized study concluded that corticosteroids have a beneficial effect in CIDP.[16] The advantages of corticosteroids are their availability and low initial costs. Unfortunately, the doses needed are often large, treatment has to be prolonged for months or years and cushingoid and various other side effects are very common.[17]

Plasma exchange (PEX) has been shown to be beneficial in two randomized trials.[18] The usefulness of PEX as a treatment for CIDP is limited by its inconvenience, requirement for hospital attendance and specially trained staff, and the occurrence of AEs. Complications, usually from the use of a central venous catheter, have been reported.[19] Therefore, PEX is now usually only considered as a third line therapy, if corticosteroids and IGIV do not prove to be effective.[20]

Some patients do not respond or become refractory or intolerant to the above described conventional treatments. Over the years, small non-randomized studies have shown possible beneficial effects of various immunosuppressive agents. A Cochrane review concluded that there is insufficient evidence at present to decide whether these immunosuppressive drugs are beneficial in CIDP or may even cause demyelinating disease. It is difficult to prove beneficial effects of these newer treatments since they only have been administered to small groups of patients who are refractory to other treatments, and often in combination with other treatments. Various treatments for CIDP are described such as azathioprine, cyclosporine, cyclophosphamide, interferons, methotrexate, mycophenolate mofetil, rituximab and etanercept.[21]

Over the last 20 years, high-dose IGIV has become an effective and safe therapeutic option for CIDP in adults and the preferred treatment in children due to the ease of its application.[22,23] The placebo-controlled ICE study in 117 CIDP patients confirmed this short-term benefit and showed for the first time sustained benefit from maintenance treatment, leading to the approval for CIDP by various authorities.[24] Other IGIV brands have meanwhile also been licensed in European countries.

The EFNS/PNS guidelines recommend that IGIV or corticosteroids should be considered for induction of treatment in CIDP in the presence of troublesome symptoms.[12] The authors recommend IGIV as an initial treatment in pure motor CIDP and PEX only in case of ineffectiveness of corticosteroids and IGIV. However, to date no study has been performed to systematically compare different IGIV dosage options in patients with CIDP.

The rationale for conducting this study is to investigate the efficacy, safety and optimal dosage of NewGam in CIDP patients, and to confirm the efficacy results that were observed in published clinical studies in order to apply for market authorization of NewGam worldwide, including the US and the EU. The study will furthermore systematically investigate different dosages of IGIV in an uncontrolled trial.

1.2 Benefit-Risk Statement

Currently, the optimal dosage of IGIV for treatment of CIDP patients is not known and has never been systematically examined. Historically, a dose of 1.0 g/kg has been used in the largest and longest placebo-controlled study that led to approval of the first IGIV for CIDP.[24] Later studies usually relied to this dosage scheme.[25] However, there may be additional benefits to individuals and society from this trial (ProCID: “**Progress in CIDP**”) in which the lack of dose response data in the literature will be addressed more extensively. There might be the possible benefit of a potential finding of this trial that a lower dose is beneficial for most patients resulting in less risk of adverse treatment effects for patients and lower costs for healthcare systems. On the other hand, it could also indicate that a higher dose might increase the number of patients who benefit from IGIV treatment, thus, reducing the number of non-responders.

The risks of IGIV administration are well documented. In general, the incidence of AEs associated with IGIV tends to increase with the rate of infusion, and thus the recommended dosage, infusion rates, and monitoring procedures should be adhered to. Patients naïve to IGIV are at higher risk compared to those who are well maintained and on regular therapy.

Patients with pre-existing risk factors for thrombotic events (such as advanced age, obesity, hypertension, diabetes mellitus and a history of vascular disease or thrombotic episodes, patients with acquired or inherited thrombophilic disorders, patients with prolonged periods of immobilization, severely hypovolemic patients, patients with diseases which increase blood viscosity) may be at risk.

When medicinal products prepared from human blood or plasma are given to a patient, the transmission of infectious agents cannot be totally excluded. This applies also to hitherto unknown pathogens. However, specific virus inactivation procedures are implemented in the manufacturing process of NewGam which are described in detail in the Investigator's Brochure.

The safety profile of NewGam is well characterized. For NewGam, the same type of adverse reactions has been seen as with other IGIV products. No new or unknown safety problems are expected to emerge which are not already described in the Investigator's Brochure.

In terms of efficacy, it can reasonably be assumed that NewGam exhibits the same effectiveness as other IGIV brands.

2 STUDY OBJECTIVES

2.1 Primary Objective

- To provide confirmatory data on the effect of 1.0 g/kg NewGam every three weeks in patients with active CIDP based on the percentage of responders at Week 24, which should corroborate the existing evidence on efficacy of IGIV in CIDP as known from published literature.

2.2 Secondary Objectives

- To assess the effect of 0.5 g/kg and 2.0 g/kg NewGam every three weeks in patients with active CIDP based on the percentage of responders at Week 24 compared to patients on 1.0 g/kg NewGam every three weeks
- To evaluate the safety of NewGam administration using various dosages in patients with CIDP
- To further evaluate the beneficial effect of three NewGam dosages in patients with CIDP by assessing different parameters/scores/scales

2.3 Exploratory Objectives

- To assess the primary and secondary objectives at three weeks after having provided rescue medication (if applicable)
- To further evaluate the beneficial effect of NewGam administration in patients with CIDP by additional assessments/scores, including quality of life (QoL) measures

3 INVESTIGATIONAL PLAN

3.1 Primary and Secondary Endpoints

3.1.1 Primary Endpoint

- Proportion of responders in the 1.0 g/kg NewGam arm at Week 24 (Termination Visit) relative to baseline (Week 0). A responder being defined as a patient with a decrease of at least 1 point on the adjusted¹ INCAT disability score (a scale from 0 to 10, from healthy to unable to make any purposeful movements with arms and/or legs)

3.1.2 Secondary Endpoints

Efficacy:

- Proportion of responders in the 0.5 g/kg and 2.0 g/kg NewGam arms at Week 24 relative to baseline at Week 0 compared to the 1.0 g/kg arm, based on the adjusted INCAT disability score
- Proportion of responders in the 0.5 g/kg and 2.0 g/kg NewGam arms at Week 24 relative to baseline at Week 0 compared to the 1.0 g/kg arm, based on the grip strength (Martin Vigorimeter) using the previously published minimum clinically important difference (MCID) cut-off of 8 kPa.[26]
- Proportion of responders in the 0.5 g/kg and 2.0 g/kg NewGam arms at Week 24 relative to baseline at Week 0 compared to the 1.0 g/kg arm, based on the I-RODS scores using the MCID concept related to the varying standard errors (MCID-SE) as recently demonstrated.[27]
- Time to first confirmed worsening on the adjusted INCAT disability scale by at least 1 point from the value at Baseline
- Mean change from Baseline (Week 0) to Termination Visit in
 - grip strength of both hands (assessed by Martin Vigorimeter) Inflammatory Rasch-built Overall Disability Sum Score (I-RODS using the concept of MCID-SE as recently reported; [Appendix 1](#)) and number of improvers
 - sum of the distal evoked amplitude of 4 right sided and 4 left sided motor nerves (peroneal, tibial, ulnar and median)
 - Pain Intensity Numeric Rating Scale (PI-NRS)
- Time to first confirmed worsening on the I-RODS scale
- Time to 1 point decrease (improvement of disability) in adjusted INCAT disability score
- Time to decrease in I-RODS scores

¹ The adjusted INCAT score is identical to the original INCAT disability score with the exception that upper extremity score changes from 0 (normal) to 1 (minor symptoms) or from 1 to 0 are excluded in determining the adjusted score, given that these changes are not considered clinically meaningful.

Safety:

Throughout the entire 24-week Dose-evaluation Phase:

- Occurrence of all adverse events (AEs)
- Short term tolerance parameters including vital signs
- Physical/neurological examination
- Laboratory parameters (hematology and clinical chemistry) and tests for viral safety
- Standard ECG (only at screening visit)

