During the 24-week Dose-evaluation Phase all patients will first receive an initial loading dose of 2.0 g/kg NewGam, followed by 7 maintenance dosages of 0.5 g/kg, 1.0 g/kg or 2.0 g/kg NewGam every 3 weeks (\pm 4 days) as they were randomized to. Two different maintenance dosages of NewGam (a higher one of 2.0 g/kg and a lower one of 0.5 g/kg) applied in the Dose-evaluation Phase will be compared with the standard dosing scheme of 1.0 g/kg every 3 weeks regarding efficacy and safety.

Due to the opportunity to receive 2.0 g/kg NewGam twice as a rescue medication and to receive standard or higher IGIV doses, it is not expected that many patients drop out. Thus, patients dropping out will not be replaced in general, but are included in the sample size calculations.

The end of the study is defined as the last visit of the last patient participating in the study.

The graph overleaf shows the study design.

Graph 3.1: Scheme of Study Design

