About half of the IGIV responders show a positive development after the initial 2.0 g/kg loading dose and the other half only after one or more additional 1.0 g/kg dose(s).[36] For comparability with the ICE trial results, the primary endpoint will be the proportion of responders to treatment, where response is defined as improvement of at least 1 point on the adjusted INCAT disability scale compared to baseline for those randomized to the 1.0 g/kg arm (the adjusted INCAT score is identical to the original INCAT disability score with the exception that upper extremity score changes from 0 (normal) to 1 (minor symptoms) or from 1 to 0 are excluded in determining the adjusted score, given that these changes are not considered clinically meaningful). Hence, a newer and better scale (I-RODS, [27]) will only be applied as secondary endpoint. In conformity with ICE and PRIMA studies, the primary endpoint will be assessed at Week 24, although the maximum response in the ICE study has been published to be after 10.2 weeks on average.[36]

Patients eligible after screening will first enter a Wash-out Phase of up to 12 weeks or until deterioration (see Section 3.2), whatever comes first, in order to select active patients who are in need of treatment. Selected patients will subsequently enter the 24-week Dose-evaluation Phase.

This Wash-out Phase and the 3-week interval between infusions have been chosen to make results comparable to the ICE and PRIMA studies.[24,25] It is in line with the “EFNS guidelines for the use of IGIV in treatment of neurological diseases”.[37] Therein it is recommended to reduce the dose in IGIV responders at intervals in order to discover whether

the patient still needs IGIV and what dosage is needed. The 3-week interval [± 4 days] chosen is also in line with the general treatment practice to administer IGIV every 2-6 weeks.

In the Dose-evaluation Phase, three NewGam dosages will be employed and the efficacy results of the higher (2.0 g/kg) and lower (0.5 g/kg) doses compared to the standard dose (1.0 g/kg) results to evaluate a potential linear dependency between dose and response. The responder rates under standard dose will be compared with the responder rates of the ICE and PRIMA studies.

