Risk minimization is achieved due to the introduction of a potential rescue treatment option: Two consecutive infusions of 2.0 g/kg NewGam at 3-week intervals [± 4 days] for all patients in the 0.5 and 1.0 g/kg NewGam arms who are either stable at Week 6 or deteriorate after Week 3 and before Week 18. The potential rescue treatment during the Dose-evaluation Phase provides the opportunity to assess if two high-dose courses of NewGam (2.0 g/kg) will convert previous non-responders (stable or deteriorating patients) in the low or medium NewGam dosage arms to responders. Patients in the 2.0 g/kg NewGam arm will drop-out if they are stable at Week 6 or deteriorating after Week 3 and before Week 21.

Measures will be taken to ensure that the sponsor, the evaluating Investigator and all parties involved in the conduct of the trial will remain blinded.

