5.5 Dose and Dosing Schedule

NewGam is available in glass bottles with different volumes of human immunoglobulin. Glass bottles of different content should be combined in order to reach the required amount of IgG (split into infusions of 0.5 g/kg and 1.0 g/kg to maintain blinding). The total amount per patient should be dosed exactly. Partially used bottles must be discarded.

All patients should be clinically assessed for being adequately hydrated prior to infusion.

In the Dose-evaluation Phase, all patients will receive a loading dose of 2.0 g/kg Newgam (administered over two consecutive days), followed by seven infusions of the maintenance dose the patient has been randomized to (0.5, 1.0 or 2.0 g/kg NewGam), also administered over two consecutive days every 3 weeks (± 4 days). If a patient is randomized to receive the low or medium NewGam dose, the same volume with the same infusion rate as would have been applied in case the patient would have been randomized to 2.0 g/kg NewGam will be used, thus

supplemented with an authorized 0.9% w/v isotonic sodium chloride solution as appropriate and detailed in the following infusion bag split to maintain the blinding:

Treatment Arms	Infusion Bag Content	
	Day 1	Day 2*
0.5 g/kg NewGam	0.5 g/kg NewGam + 0.5 g/kg saline	1.0 g/kg saline
1.0 g/kg NewGam	0.5 g/kg NewGam + 0.5 g/kg NewGam	1.0 g/kg saline
2.0 g/kg NewGam	0.5 g/kg NewGam + 0.5 g/kg NewGam	1.0 g/kg NewGam

* Volume of Day 2 may be split up using 2 bags

The following infusion schedule must be adhered to in the Dose-evaluation Phase [all doses per kg body weight; rescue treatment only for patients who had been on 0.5 or 1.0 g/kg NewGam before, patients on 2.0 g/kg before will drop-out]:

1. Patients deteriorating* after Week 3 and before Week 6 or being stable at Week 6**

Week 0	Week 3	Week 6	Week 9	Week 12
2.0 g (LD)	0.5g 1.0 g	2.0 g (RT)	2.0 g (RT)	EOS
	2.0 g	EOS		

2. Patients deteriorating* after Week 6 and before Week 9

Week 0	Week 3	Week 6	Week 9	Week 12	Week 15
2.0 g (LD)	0.5g 1.0 g	0.5g 1.0 g	2.0 g (RT)	2.0 g (RT)	EOS
	2.0 g	2.0 g	EOS		

3. Patients deteriorating* after Week 9 and before Week 12

Week 0	Week 3	Week 6	Week 9	Week 12	Week 15	Week 18
2.0 g (LD)	0.5g 1.0 g	0.5g 1.0 g	0.5g 1.0 g	2.0 g (RT)	2.0 g (RT)	EOS
	2.0 g	2.0 g	2.0 g	EOS		

4. Patients deteriorating* after Week 12 and before Week 15

Week 0	Week 3	Week 6	Week 9	Week 12	Week 15	Week 18	Week 21

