10.1. Primary Efficacy Variable Analysis

The primary efficacy variable is the proportion of responders in the 1.0 g/kg NewGam arm at Week 24 (Termination Visit) relative to baseline (Week 0). A responder being defined as a patient with a decrease of at least 1 point on the adjusted INCAT disability score.

Confirmatory statistical testing of the primary endpoint will be done by constructing the 95% Wilson-Score confidence interval for the proportion of responders, and comparing the lower confidence limit with the predefined threshold of 0.42. This corresponds to a one-sided test of the following pair of hypotheses at the α =0.025 confidence level.

 H_0 : R < 0.42

 $H_1: R \ge 0.42$

Where *R* is the proportion of responders i.e. the number of patients in the FAS who are responders according to the abovementioned definition, divided by the total number of patients in the FAS.

This evaluation will also be presented for the PPS to assess the robustness of the primary study endpoint with respect to protocol deviations.

To assess and compare the primary efficacy endpoint also between the different dose groups, and also between the randomization strata (by dose group and over all dose groups) the proportion of responders will be presented side-by-side, including the 95% confidence intervals.

The time to first response and time to first worsening will be examined and presented by means of a Kaplan-Meier analysis.

Additional analyses, such as logistic regression- will be deployed to further examine any noteworthy differencesin an exploratory manner. The logistic regression model for analysis of response will include dose group, randomization stratum and CIDP variant (typical vs. atypical) as factors and baseline score as covariate. Odds ratios will be calculated to compare response rates between the factor levels, these will be presented together with 95% confidence intervals.

Moreover the proportion of responders after having provided rescue medication will be calculated with respect to all patients who received rescue medication and will be presented by dose group and overall, together with 95% confidence intervals.

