10.2. Secondary and Exploratory Efficacy Variable Analysis

All efficacy endpoints detailed in section 3.2 will be summarized by means of descriptive statistics, presented graphically as appropriate, and listed in full detail. Tables and graphs will allow for direct comparison of the different dose groups. If data are tabulated by dose group, the presentations will also include a total category, summarizing the data of all subjects in any of the dose groups. Tables for changes from baseline will include 95% confidence intervals of the mean for continuous secondary endpoints (I-RODS total score; grip strength; MRC sum score; FSS total score; NCS measurements; QoL scores) and 95% confidence intervals for the median for ordinal scales (INCAT disability sore, PI-NRS), calculated with PROC univariate option CIQUANTDF.

Similar analyses as for the primary endpoint will be performed for response variables defined based on secondary endpoints (I-RODS, grip strength, MRC sum score). These will include analysis of response rates and 95% confidence intervals, logistic regression models using the same factors as for the primary endpoint, Kaplan-Meier analyses for time to response and time to first worsening and response rates after having provided rescue medication.

Moreover, ANCOVA models will be applied for continuous secondary endpoints (I-RODS total score; grip strength; MRC sums score; FSS total score; NCS measurements; QoL scores). These ANCOVA models for changes from baseline to end of study will include dose group, randomization stratum and CIDP variant as factors and baseline value of the score/measurement as covariate. ANCOVA models will be used for calculation of least square means in various subgroups as well as for calculation of difference in least square means between the factor levels. All least square means will be presented together with 95% confidence intervals.

Any deterioration during the dose evaluation phase will be listed. Moreover, deteriorations during dose evaluation will be presented by dose group and by their effect on subject disposition (discontinuation, rescue medication).

11. Safety and Tolerability Analyses

The analysis of safety assessments in this study will be presented for the SAF.

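### Time to first INCAT response can show at most the loading dose plus one maintenance infusion, and a date-based Kaplan-Meier estimate of it would overstate the proportion responding

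*Protocol*

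**What the plan says.** Protocol 3.1.2 lists the secondary endpoint "Time to 1 point decrease (improvement of disability) in adjusted INCAT disability score". SAP 10.1 gives the method: "The time to first response and time to first worsening will be examined and presented by means of a Kaplan-Meier analysis". SAP 10.2 states the purpose for all efficacy endpoints: "Tables and graphs will allow for direct comparison of the different dose groups".

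Four design rules determine when this event can occur:

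- **Common start.** Under Protocol 3.2, "all patients will first receive an initial loading dose of 2.0 g/kg NewGam, followed by 7 maintenance dosages" at the randomized dose.
- **Scoring before dosing.** Protocol 6.1.3 lists adjusted INCAT among the pre-infusion assessments at each infusion visit.
- **Week 6 rule.** Protocol 3.3.1 gives rescue to patients in the 0.5 and 1.0 g/kg arms "who are either stable at Week 6 or deteriorate after Week 3 and before Week 18". For the top dose it says "Patients in the 2.0 g/kg NewGam arm will drop-out if they are stable at Week 6" or deteriorate. Protocol 5.5 and 5.7 define stable as an unchanged adjusted INCAT score.
- **Censoring.** SAP 8.4 allows no response after rescue. It censors time to first response at the rescue start date, or at the termination visit if there was neither response nor rescue.

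Protocol 6.1.5 allows ±4 days on each 3-week interval.

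**The concern.** A Kaplan-Meier plot by dose in a 24-week trial invites the reader to treat it as evidence on 24 weeks of maintenance dosing. The protocol's background encourages this. Section 3.3.1 says "About half of the IGIV responders show a positive development after the initial 2.0 g/kg loading dose" and the rest only after one or more further doses, and it reports an average time to maximum response of 10.2 weeks in the earlier placebo-controlled trial. A reader would expect late first responses, but under these rules almost none can be recorded. Overlapping curves could then be taken as no dose effect, although they carry no information on most of the maintenance infusions.

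The second issue is estimation. Patients known not to have responded at Week 6 leave the risk set on dates interleaved with the Week 6 responses. Kaplan-Meier treats them as if they might still respond later, which the design rules out.

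**Working it through.** The documents give no figure for this endpoint, so there is none to reproduce.

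**Step 1: possible event times.** Take each patient's change from baseline at Weeks 3 and 6.

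| Week 3 | Week 6 | Outcome for first response |
|---|---|---|
| Improved | any | Event at Week 3 |
| Unchanged or worse | Improved | Event at Week 6 |
| Unchanged or worse | Unchanged | Censored at Week 6: rescue (0.5, 1.0 g/kg) or end of study (2.0 g/kg) |
| Unchanged or worse | Worse than at Week 3 and than baseline | Same as the row above |
| Worse | Worse than baseline, no worse than at Week 3 | Not literally covered by the trigger wording in Protocol 3.3.1 |

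The last row is the only route to a later first event under full adherence. Protocol 6.2.1 (2.0 g/kg patients deteriorating by Week 6) and 6.1.3 (Week 24 visit described as being for responders) suggest such patients were not expected to continue. A missed Week 6 visit, or rescue not given, could add isolated late events.

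**Step 2: dose information at each step.** At Week 3 all arms have had only the loading dose, so that step is equal across arms in expectation. At Week 6 patients have had one maintenance infusion, a genuine randomized contrast. Infusions 2 to 7 contribute nothing.

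To size this, suppose a log-rank test were run (none is planned). With two event times, z = (U3 + U6)/√(V3 + V6), where U is observed minus expected events and V its variance. U3 has expectation zero, but V3 still enters the denominator and dilutes the contrast. Assume 20–40% respond at Week 3 in both arms (the rates here are assumptions), and use a two-sided 5% level with 20,000 simulations per setting:

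| Week 6 response among those at risk | 35 vs 70 patients | 35 vs 35 patients |
|---|---|---|
| 20% vs 40% | 16–27% | 12–22% |
| 10% vs 40% | 30–53% | 24–44% |
| Equal (30%) | about 5% | about 5% |

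In the unequal settings with 35 vs 70 patients, Week 3 events are 43–69% of all events.

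**Step 3: bias from date-based censoring.** Assume 35% respond at Week 3 and 43% of the rest at Week 6.

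- True proportion responding: 0.35 + 0.65 × 0.43 = 0.63.
- Kaplan-Meier with everyone on the nominal day, events counted before censorings: 1 − 0.65 × 0.57 = 0.63, so no bias.
- Kaplan-Meier on actual dates, with Week 6 visits spread evenly over the nine days of the window: each day 43% of that day's attenders have the event and 57% are censored. With k days remaining, the day's factor is 1 − 0.43/k. The product for k = 9 down to 1 is 0.952 × 0.946 × 0.939 × 0.928 × 0.914 × 0.893 × 0.857 × 0.785 × 0.570 = 0.245. The estimate is 1 − 0.65 × 0.245 = 0.84.
- With visits spread over only three days: 0.857 × 0.785 × 0.570 = 0.383, and the estimate is 1 − 0.65 × 0.383 = 0.75.

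The estimate thus runs from 63% to 84% for the same patients, depending only on visit scheduling.

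**The case against.** The other side has several sound points.

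- **A reader might infer that the curves cannot compare doses at all.** The documents do not support that. The Week 6 step is a randomized comparison of one infusion at three doses; Step 2 shows its information is low but not zero.
- **A reader might infer that the limit holds however rescue is handled.** It does not. Protocol 3.1.2 has no censoring rule, and rescue patients keep their visits and INCAT scores (Protocol 6.1.4, 7.2.1.1). If decreases after rescue counted, first events could occur at Weeks 9 and 12. The limit comes from SAP 8.4 together with the Week 6 rule.
- **A reader might infer that later loss of response goes unmeasured on INCAT.** It does not. The first secondary endpoint is the Week 24 INCAT responder proportion by arm, in which SAP 8.4 counts rescue, discontinuation and lost response as non-response. Protocol 9.2.2 adds confidence intervals for the differences, and SAP 10.2 tabulates deteriorations by dose group and their effect on disposition. What is missing is an INCAT time-to-loss endpoint: time to worsening needs a score above baseline, and the only time-to-loss endpoint is on the MRC score, taken in this phase only at Weeks 0, 12 and termination.
- **The planned Week 24 comparison already does well.** An illustration assumed 35 vs 70 patients, 35% responding at Week 3, then 43% (1.0 g/kg) and 35–43% (0.5 g/kg) of the rest at Week 6, and loss per later visit of 2–3% vs 10–15%. The Week 24 comparison detected the difference in 50–94% of simulations, against 40–89% for a time-to-failure endpoint in all patients, and was ahead in every setting. Such an endpoint is therefore not needed to answer the dose question.

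One objection fails: that reporting Week 3 and Week 6 proportions only repeats the curve. Step 3 shows that a date-based curve need not reproduce them.

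**Conclusion.** The point holds in limited form. If the Week 6 rule is followed and SAP 8.4 censoring applied, first INCAT responses fall essentially at Week 3 or Week 6. The curves then reflect the loading dose plus at most one maintenance infusion and are silent on infusions 2 to 7. The exceptions are non-adherence and the uncovered patient in the last row of the first table.

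If Kaplan-Meier is run on actual dates, it also overstates the response proportion, by up to about 21 percentage points (84% against 63%) in the illustration. That size rests on assumed response rates and an even spread of visits. The direction follows from censoring known non-responders among the events, and the bias vanishes if nominal visits are used with events counted before censorings.

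This concerns the labelling and estimation of one descriptive secondary endpoint. The primary endpoint, its threshold and its sample size are unaffected.

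**What to change.** In SAP 8.4 and 10.1, before unblinding:

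1. Report first INCAT response by arm as the proportions first responding at the nominal Week 3 and Week 6 visits. Use all patients in the arm as denominator, and count patients who start rescue or exit as non-responders.
2. State beside the result that it reflects the loading dose plus at most one maintenance infusion.
3. Name the Week 24 responder proportion as the main dose comparison.
4. Optionally, add a supplementary time from Week 3 to loss of INCAT response by arm, among patients who had responded at Week 3. Loss is a score back at or above the Week 0 value, rescue, or efficacy exit. Membership is fixed before the arms diverge, so the arms stay comparable. The groups would be small: at an assumed 35% response, about 12 of 35 and 25 of 70 patients.

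Cost: one planned curve is replaced and one derived variable may be added, from INCAT visits already scheduled. No new data or patients are needed, and the treatment rules do not change.
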